8.5.3 Analysis of Secondary Endpoints

For the secondary endpoints, subject pregnancy result (positive/negative) and subject with confirmed pregnancy (yes/no), the pregnancy rate at PET Day 14 and ongoing pregnancy rate at PET Days 70-84 will be estimated and compared using logistic regression model including Embryo Transfer Day (Day 5 PR or Day 7 PR), age and number of follicles at baseline as covariates. Estimates of odds ratio, confidence intervals and relevant p-values will be presented for each endpoint.

8.5.4 Analysis of Safety and Other Endpoints

Device incidents will be summarized using frequency and percentages for two treatment groups.

Clinical laboratory assessments (E₂ and P₄, etc.) will be presented in listings appropriately.

Substance Code Clinical Performance and Safety Investigation of ENDOmetrial Washing
MEdical DEvice Forielle
Protocol Number MS 700623_0009

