4.2 Secondary Objectives

The secondary objectives of the study are to:

- Determine the Pregnancy Rate at PET Day 14
- Determine the Ongoing Pregnancy Rate during PET Days 70 to 84
- Assess the safety of Forielle by report of device incidents

Substance Code Clinical Performance and Safety Investigation of ENDOmetrial Washing
MEdical DEvice Forielle
Protocol Number MS 700623_0009

5 Investigational Plan

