6.5.5 Management of Specific Adverse Events or Adverse Drug Reactions

There are no adverse events expected with the use of this device except hypersensitivity to the Forielle components, as indicated in the IFU. If hypersensitivity to Forielle occurs, the Investigator will follow the IFU and standard of care treatment.

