7.4 Assessment of Safety

Safety of Forielle will be assessed through the recording and reporting of medical device incidents.

In addition, any Adverse Event (AE) or Serious Adverse Event (SAE) related to the conduct of the study that would occur in a subject participating in the clinical trial will be recorded and reported through AE CRF. The analysis of these AEs/SAEs should be used to update the Forielle Risk Assessment as well as Instruction For Use.

Of note, given the design of this study and the reporting period for safety surveillance, assessment of serious adverse device effects in offspring of subjects participating in the clinical trial is not applicable (see Section 7.4.1).

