7.4.3 Medical Device Incidents

Device Incidents will be reported as described below.

7.4.3.1 Definition of Medical Device Incident (MEDDEV 2.12-1, Rev. 8, adapted to definitions above)

A medical device incident is 'any malfunction or deterioration in the characteristics and/or clinical performance of a device, as well as any inadequacy in the labelling or the IFU which, directly or indirectly, might lead to or might have led to the death of a patient, or USER or of other persons or to a serious deterioration in their state of health'. A medical device incident that would require reporting include:

Substance Code Clinical Performance and Safety Investigation of **ENDO**metrial Washing
MEdicinal **DE**vice Forielle
Protocol Number MS 700623_0009

- a) Serious public health threat: Any event type which results in imminent risk of death, serious deterioration in state of health, or serious illness that requires prompt remedial action (MEDDEV 2.12-1 rev.8).
- b) Death or UNANTICIPATED serious deterioration in state of health of a subject that resulted in
 - 1) A life-threatening illness or injury, or
 - 2) A permanent impairment of a body structure or a body function, or
 - 3) In-patient or prolonged hospitalization, or
 - 4) Medical or surgical intervention to prevent life-threatening illness or injury or permanent impairment to a body structure or a body function
- c) Other events: events that have an established link between the device and the event

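### Section 8 specifies a safety summary for device incidents only, so non-serious harm after a correctly performed wash can be left out and no adverse-event comparison by arm is planned

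*Combined protocol and SAP*

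**What the plan says.** **Objective, endpoint and analysis.** Section 4.2 sets the safety objective as "Assess the safety of Forielle by report of device incidents". Section 8.3.2 lists device incidents as the only safety item among the secondary endpoints. Section 7.4 opens with "Safety of Forielle will be assessed through the recording and reporting of medical device incidents". Section 8.5.4, like the synopsis, gives the analysis in one sentence: "Device incidents will be summarized using frequency and percentages for two treatment groups".

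**Definition.** Section 7.4.3.1 begins with "any malfunction or deterioration in the characteristics and/or clinical performance of a device, as well as any inadequacy in the labelling or the IFU", where the fault might lead to death or serious deterioration in health. A list of reportable incidents follows. Besides serious public health threats (a), it contains (b) "Death or UNANTICIPATED serious deterioration in state of health of a subject that resulted in" a life-threatening illness, permanent impairment, hospitalisation or a preventive intervention, and (c) "Other events: events that have an established link between the device and the event".

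**Expected harm.** Section 6.5.5 says: "There are no adverse events expected with the use of this device except hypersensitivity to the Forielle components".

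**Adverse events.** Section 7.4.2.3 has AEs that relate to study conduct recorded from the start of stimulation to study exit. They go on a form separate from the incident form, with onset and resolution dates, severity, seriousness, relationship and outcome. Section 7.4 adds: "The analysis of these AEs/SAEs should be used to update the Forielle Risk Assessment as well as Instruction For Use".

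**General statements.** The synopsis says variables will, as appropriate, be summarised descriptively by visit and treatment group. Section 8.5.1 promises by-subject listings and leaves table details to a separate SAP, which is not in the supplied text. The Safety set in 8.4 holds only randomised women in whom a wash was attempted.

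**The concern.** Safety is in the trial's title, and section 3.1.2 gives confirming clinical safety as a reason for the study. The variable chosen to carry that aim is a vigilance term. It is built to catch device faults and serious events, not the ordinary harms of an intrauterine procedure. Pain, bleeding, a mild infection or a mild reaction after a properly performed wash need not qualify as an incident.

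The randomised control group also contributes nothing to this variable, although a between-arm contrast is the main thing a randomised trial offers for safety. At stake is whether the trial can give any rate or contrast for non-serious harm, when much of the raw information is already on the AE form.

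**Working it through.** **1. The plan's own figures.** No safety figure is stated. The sample size gives the scale: 916 × 2 = 1,832, and 1,832 / 0.85 = 2,155.3, rounded up to 2,156, so 1,078 women per arm. Two-look power with 916 per arm, boundaries 2.96259 and 1.96857 and the continuity correction comes to 0.8002, against 0.80025 stated. These figures hold and this point does not touch them.

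**2. What the definition admits.** Take events that follow a correctly performed wash with a sound device and adequate labelling:

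| Event | Head definition | Item (b) | Item (c) |
|---|---|---|---|
| Non-serious pain, bleeding or infection, link not established | No | No, not serious | No |
| The same, link established | No | No, not serious | Yes |
| Hypersensitivity, the one expected event | No | No, anticipated | Only if a link is established |
| Unanticipated serious deterioration | No | Yes | If a link is established |

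The last two columns count only if the list can stand without the head definition. If the head definition governs, none of the four rows is an incident. If the list stands alone, serious unanticipated harm and device-linked events are in. The text does not say which reading applies. The first row is out on either reading.

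**3. The control column.** A control woman has no device. Section 7.4.3.2 has subjects asked about incidents associated with use of Forielle, and the device-recording row of the schedule, though badly read from the PDF, is labelled for the Forielle group. The control count is therefore zero by construction, apart from a control woman washed in error, whom the Safety set counts under the procedure received. If the summary uses the Safety set, the control column has no denominator either.

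**4. The adverse-event route.** The AE row of the schedule and section 7.4.2.3 are not restricted by arm, so study-conduct AEs are recorded in both. Section 7.4 relies on their analysis. Section 8 gives no table, analysis set or comparison for them, whereas 8.5.4 does name listings for E2 and P4. The DMC does not fill the gap, because section 8.6 gives its purpose as verifying the reliability of the primary endpoint.

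**5. Scale (all event rates are assumed; the documents give none).**
- Zero incidents among n washed women gives a one-sided 95% upper limit of 1 − 0.05^(1/n): 0.28% for n = 1,078 and 0.33% for n = 916. The limit applies only to what the definition admits.
- Suppose the wash caused a non-serious event with no established link. At 0.5%, 1% and 2%, 1,078 women give 5.4, 10.8 and 21.6 cases; 916 women give 4.6, 9.2 and 18.3.
- For what an AE comparison could show, solve n = [1.96·√(2p̄(1−p̄)) + 0.8416·√(p₁(1−p₁)+p₂(1−p₂))]² / (p₂−p₁)² for p₂ at n = 916 per arm (two-sided 0.05, 80% power, p̄ the mean of p₁ and p₂). Control rates of 1%, 2% and 5% give detectable washed-arm rates of about 2.8%, 4.3% and 8.3%.

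**The case against.** The best defence is that this is a deliberate choice. The study is post-marketing follow-up of a CE-marked Class IIa device, run as a commitment to the certifying body, so a vigilance endpoint is natural. Items (b) and (c) reach beyond malfunction. Section 7.4.3.2 asks the investigator to judge both seriousness and relationship to the device, which suggests that non-serious incidents could be recorded. The synopsis promises descriptive summaries by group, 8.5.1 promises listings, and the separate SAP may contain AE tables. The AE form covers only events tied to study conduct, as judged by investigators who know the allocation, so a comparison from it would not be a clean all-cause contrast.

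Much of this stands, and it rules out four stronger readings:
- A reader might infer that adverse events get no analysis at all. Section 7.4 refers to one, and the general summary and listing statements could cover them.
- A reader might infer that an incident can only be a malfunction or labelling fault. Items (b) and (c) say otherwise, and (c) does not require the link to have been known before the trial.
- A reader might infer that no harm from a working wash could surface. Serious unanticipated or device-linked harm can be an incident, and other recorded events would be listed.
- A reader might infer that the device would then be declared safe. Section 8.5.4 is descriptive with no decision rule, and section 10.7.1 requires the report to state limitations.

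The defence does not supply a specified summary of AEs or SAEs by arm. The choice of objective and endpoint is made in the protocol itself, and listings give no rate and no contrast. Nor does it make the incident summary comparative.

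**Conclusion.** The concern holds in a limited form. Device incidents are the only safety endpoint and the only safety summary that section 8 specifies. Their definition and list need reconciling, non-serious harm without an established device link falls outside them on either reading, and controls contribute zero by construction. The AE/SAE analysis that section 7.4 relies on is not specified by arm.

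The size is illustrative: about 5 to 22 of 1,078 washed women if the wash caused such an event in an assumed 0.5% to 2%, taking every woman randomised to Forielle as washed. The conclusion rests on the supplied text; a separate SAP with AE tables by arm would meet part of it. Neither the primary analysis nor the sample size is affected. This is a worthwhile, inexpensive improvement, not an error that invalidates the trial.

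**What to change.** - In 4.2, 8.3.2 and 8.5.4, add AEs and SAEs with onset on or after the Day 2 retrieval. Tabulate them by arm as women with at least one event, by term, severity and seriousness, with the risk difference and its 95% CI.
- Name an analysis set that includes control women, for example all randomised women who undergo oocyte retrieval, grouped by procedure received. The Safety set in 8.4 cannot serve.
- Keep device incidents, as a Forielle-only vigilance summary, and drop the two-group wording for them.
- Reconcile the head definition in 7.4.3.1 with its list, stating whether the items in the list count without a malfunction or labelling fault.

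The cost is protocol and SAP wording and a few tables from data already on the AE form. The drawback should be stated with the tables: they are limited to events that unblinded investigators recorded as related to study conduct, so the comparison should be read descriptively. An all-cause comparison would need wider collection, which this change does not provide.

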8.6 Interim and Additional Planned Analyses

One interim analysis is planned and a Data Monitoring Committee (DMC) will review and give advice to the sponsor regarding the study conduct. The DMC will be comprised of a statistician and physician not part of the study and will be appointed prior to the planned interim analysis. The purpose of the DMC is to verify the reliability of the primary endpoint since the study is unblinded to the study investigator. Detailed procedures will be described in a DMC charter.

Interim analysis on PET Days 21 to 28 data will be conducted when 1,078 subjects have been through treatment procedure and followed for 21 to 28 days after embryo transfer for the primary analysis. An O'Brien-Fleming type boundary will be used to determine the nominal significance level with overall 5% two-sided significance level i.e., the nominal significance level for the interim analysis will be 0.003. Based on the interim finding, the DMC may recommend to stop the subject enrolment early for clinical performance considerations or to continue the study as planned. No further results of the interim analysis will be made available by the DMC until final analysis is done.

The final analysis will be done when 2,156 subjects have been through treatment procedure and followed for 70 to 84 days post embryo transfer and complete all the protocol planned procedures and the O'Brien-Fleming boundary will be used to determine the nominal significance level with overall 5% two-sided significance level i.e. the nominal significance level for the final analysis will be 0.049.

9 Ethical and Regulatory Aspects

9.1 Responsibilities of the Investigator

The Investigator is responsible for the conduct of the trial at the sites and will ensure that the trial is performed in accordance with this protocol, the ethical principles outlined in the Declaration of Helsinki and any other applicable regulations. The Investigator must ensure that only subjects who have given informed consent are included in the trial.

9.2 Subject Information and Informed Consent

An unconditional prerequisite for each subject prior to participation in the trial is written informed consent, which must be given before any trial-related activities are carried out. Adequate information must therefore be given to the subject by the Investigator or an appropriate designee (if local regulations permit) before informed consent is obtained.

A subject information sheet must be prepared in the local language in accordance with local regulations and will be provided by the Sponsor for the purpose of obtaining informed consent. In addition to providing this written information to a potential subject, the Investigator or a designate will inform the subject verbally of all pertinent aspects of the trial, using language chosen so that the information can be fully and readily understood by laypersons. The subject

Substance Code Clinical Performance and Safety Investigation of ENDOmetrial Washing
MEdical DEvice Forielle
Protocol Number MS 700623_0009

will be given sufficient time to read the information and the opportunity to ask questions and to request additional information and clarification.

Only the Investigator and sub-investigators may inform the subject about the trial and sign the Informed Consent Form (ICF), as above.

After the information is provided by the Investigator, the ICF must be signed and dated by the subject and the Investigator.

The signed and dated declarations of informed consent are to remain at the Investigator's site, and must be safely archived so that the forms can be reviewed during study monitoring and auditing. A copy of the signed and dated ICF should be provided to the subject.

Whenever important new information becomes available that may be relevant to informed consent, the Investigator will revise the subject information sheet and any other written information to be provided to the subjects and submit them to the IEC for review and opinion. Using the approved revised subject information sheet and other written information, The Investigator will explain the changes to the previous version to each trial subject and obtain new written consent for continued participation in the trial. The subject will be given sufficient time to read the information and the opportunity to ask questions and to request additional information and clarification about the changes.

9.3 Subject Identification and Privacy

A unique number will be assigned to each subject immediately after informed consent has been obtained. This number will serve as the subject's identifier in the trial as well as in the clinical trial database. All subject data collected in the trial will be stored under the appropriate subject number. Only the Investigator will be able to link trial data to an individual subject via an identification list kept at the sites. For each subject, original medical data will be accessible for the purposes of source data verification by the Monitor, audits and regulatory inspections, but patient confidentiality will be strictly maintained.

Data protection and privacy regulations will be observed in capturing, forwarding, processing, and storing subject data. Subjects will be informed accordingly, and will be requested to give their consent on data handling procedures in accordance with national regulations.

9.4 Emergency Medical Support and Subject Card

Subjects will be provided with an Emergency Medical Support card by the Sponsor for use during trial participation in order to provide clinical trial subjects with a way of identifying themselves as participating in a clinical trial, and to give health care providers access to any information about this participation that may be needed to determine the course of medical treatment for the subject.

The first point of contact for all emergencies will be the clinical trial Investigator caring for the subject. The Investigator agrees to provide his or her emergency contact information on the card

Substance Code Clinical Performance and Safety Investigation of ENDOmetrial Washing
MEdical DEvice Forielle
Protocol Number MS 700623_0009

for this purpose. If the Investigator is available when an event occurs, they will answer any questions and any subsequent actions will follow the standard process for Investigator oversight.

9.5 Clinical Trial Insurance and Compensation to Subjects

Insurance coverage will be provided for the country participating in the trial, as per local and country legislation. Insurance conditions shall meet good local standards, as applicable.

9.6 Independent Ethics Committee

Prior to commencement of the trial at a given site, this clinical trial protocol will be submitted together with its associated documents to the responsible IEC for its favourable opinion or approval, which will be filed in the Investigator Site File. A copy will be filed in the Trial Master File.

The IEC will be asked to document the date of the meeting at which the favourable opinion or approval was given and the members and voting members present. Written evidence of favourable opinion or approval that clearly identifies the trial, the clinical trial protocol version and the Subject Information and ICF version reviewed should be provided. Where possible, copies of the meeting minutes should be obtained.

Amendments to this clinical trial protocol will also be submitted to the concerned IEC, before implementation of substantial changes (see Section 10.6). Relevant safety information will be submitted to the IEC during the course of the trial in accordance with national regulations and requirements.

9.7 Competent Authorities

The clinical trial protocol and any applicable documentation (e.g., IFU and ICF) will be submitted or notified to the Competent Authorities in accordance with local and national regulations.

10 Trial Management

10.1 Protocol Deviation and Deviation Reporting

A protocol deviation occurs when an investigator and/or trial site personnel do not conduct the trial according to the clinical protocol. Investigators must maintain accurate, complete and current records related to the trial. This includes source documents showing the dates and reasons for each deviation from the clinical protocol. Depending upon the nature of the protocol deviation, expedited reporting to the reviewing IEC, according to the reporting requirements of the IEC, and prior approval from the sponsor may be required.

If the sponsor or its designate determines that an investigator is not complying with the executed clinical research agreements, the clinical protocol, applicable regulations, or the requirements of

Substance Code Clinical Performance and Safety Investigation of ENDOmetrial Washing
MEdical DEvice Forielle
Protocol Number MS 700623_0009

the reviewing IEC, prompt action will be taken to secure compliance. In addition, the participation of an investigator may be terminated.

10.2 Case Report Form Handling

Refer to the Study Manual for eCRF handling guidelines. The main purpose of the eCRF is to obtain data required by the clinical trial protocol in a complete, accurate, legible, and timely manner. The data in the eCRF should be consistent with the relevant source documents.

The Investigator or designee is responsible for ensuring that the data collected in the course of this trial is accurate and documented appropriately on all applicable forms. They will then be processed, evaluated, and stored in anonymous form in accordance with applicable data protection regulations. The Investigator must ensure that the eCRFs and any other associated documents forwarded to the Sponsor or its designated organization contain no mention of any subject names.

The data will be entered into a validated database. The Sponsor or its designee will be responsible for data processing in accordance with PPD data management procedures. Database lock will occur once quality control and quality assurance procedures have been completed. PDF files of the eCRFs will be provided to the Investigators at the completion of the trial.

10.3 Source Data and Subject Files

The Investigator must keep a file (medical file, original medical records) on paper or electronically for every subject in the trial. It must be possible to identify each subject by using this subject file. This file will contain the demographic and medical information for the subject listed below and should be as complete as possible:

- Subject's full name, date of birth, sex, height, weight
- Medical history and concomitant diseases
- Prior and concomitant therapies (including changes during the trial)
- Trial identification, that is, the Sponsor trial number for this clinical trial, and subject number
- Dates for entry into the trial (informed consent) and visits to the site
- Any medical examinations and clinical findings predefined in this clinical trial protocol
- All AEs
- Date that the subject left the trial including any reason for early withdrawal from the trial

All documents containing source data must be filed, including, but not limited to: transvaginal ultrasound results, hormones administered and laboratory results. Such documents must bear the subject number and the date of the procedure. If possible, this information should be printed by the instrument used to perform the assessment or measurement. As necessary, medical evaluation

Substance Code Clinical Performance and Safety Investigation of ENDOmetrial Washing
MEdical DEvice Forielle
Protocol Number MS 700623_0009

of such records should be performed; all evaluations should be documented, signed, and dated by the Investigator.

Electronic subject files will be printed whenever the Monitor performs source data verification. Printouts must be signed and dated by the Investigator, countersigned by the Monitor and kept in a safe place at the site.

